Aim 1: To examine whether high levels of estradiol augment the effect of THC on subjective anxiety, heart rate, blood pressure and salivary cortisol in females. To test this, female occasional cannabis users will receive a single dose of THC (0, 15 mg) during either the early follicular phase (days 1-8) when estradiol levels are low, or during the late follicular phase (days 9-14) when estradiol levels are high. Participants will attend two experimental sessions separated by at least four days, to allow for clearance of the drug. Plasma levels of estradiol, progesterone, and endocannabinoids, as well as salivary cortisol, physiological measures and subjective mood ratings will be obtained at the beginning of all three sessions. During the sessions, physiological measures, subjective ratings of drug effects and mood, and salivary cortisol will be obtained at regular intervals after drug consumption. I hypothesize THC will produce a greater increase in subjective anxiety, heart rate, blood pressure and salivary cortisol during the late follicular phase, and that this will be correlated with higher circulating levels of estradiol.

Aim 2: To examine whether low levels of circulating endocannabinoids augment the effects of THC on subjective anxiety, heart rate, blood pressure and salivary cortisol in females. To test this, the plasma samples mentioned above will also be analyzed for endocannabinoids, anandamide (AEA) and 2-arachidonoylglycerol (2-AG) levels. Baseline AEA and 2-AG levels will be compared to THC-induced increases in subjective anxiety, heart rate, blood pressure and salivary cortisol. I hypothesize females with lower endocannabinoid levels will exhibit greater THC-induced increases in subjective anxiety, heart rate, blood pressure and salivary cortisol levels.

Aim 3: To evaluate determine whether subjective anxiety mediates the physiological stress response after THC. To test this, I will use a multilevel longitudinal mediation model to analyze the collected data. Our independent variables will include within-subjects drug dose and between subjects estradiol (EFG or LFG), AEA and 2-AG levels. Our mediator variable will be subjective anxiety across session time. Our dependent outcome measures include heart rate, blood pressure and salivary cortisol across session time. A multilevel

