For this study we will use a mixed within- and between subject design to examine effects of THC (0 and 15 mg) in two groups of female occasional cannabis users: women tested in the early follicular phase of their menstrual cycle (EFG; N=30) and women tested in the late follicular phase (LFG; N=30). Occasional cannabis users will be defined as individuals who have used cannabis 10 or less occasions in the past thirty days. Females will be randomly assigned EFG or LFG groups. EFG women will be tested 1 to 8 days since the first day of menstruation and LFG women between days 9 and 14. Subjects will attend two four-hour experimental sessions in which they receive THC (15 mg THC) or placebo in counterbalanced order under double blind conditions. Plasma and saliva samples will be obtained before capsule consumption at the start of each session for baseline hormone, endocannabinoid and cortisol levels. The primary outcome measure is salivary cortisol, which will be measured both at baseline and periodically post-drug consumption. Secondary outcome measures include heart rate, blood pressure, body temperature, subjective drug effects (i.e. "feel drug effect"), and THC-induced anxiety. For Aim 1 we will examine THC-induced increases in cortisol in relation to baseline estradiol levels. For Aim 2 will examine THC-induced cortisol in relation to baseline endocannabinoid levels. For Aim 3 we will examine THC-induced increases in heart rate and subjective drug effects relative to THC-

induced increases in cortisol. The study will be approved by the Institutional Review Board at the University of Chicago, in accordance with the Code of Federal Regulations (Title 45, Part 46) adopted by the National Institutes of Health and the Office for Protection from Research Risks of the US Federal Government. The studies will be conducted in accordance with the Helsinki Declaration of 1964 (revised 1989) and the National Advisory Council on Drug Abuse Recommended Guidelines for the Administration of Drugs to Human Subjects.

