Orientation Session Participants will first participate in a 1-hour orientation session to provide informed consent, agree to the study conditions described above, complete the Trait Anxiety Inventory (Spielberger et al. 1971) and the Anxiety Sensitivity Inventory (Reiss et al. 1986), and practice questionnaires that will be administered throughout the sessions. Participants will be instructed to refrain from any use of drugs or alcohol for 24 before the experimental sessions. They will be advised that they must pass urine tests on the days of their experimental sessions for recent drug use including cannabis, and to pass these tests they should abstain from use for one week if they are light users (1-2 times per week) and for two weeks if they are heavier users (e.g., every other day). They will be told to have a normal night's sleep before the session and abstain from eating for at least 6 hours prior to their session. For blinding purposes, subjects will be told the capsules used in the study may contain a placebo, stimulant, cannabinoid-like drug, or sedative. The reason for blinding is we wish to study the pharmacological effects of this drug, without the possible confound of expectancies. We and others have shown that expectancies influence responses to drugs, in ways that might obscure true biological differences in the effects of the drug (see Mitchell et al. 1996; Kirk et al. 1998; Metrik et al. 2009; Heinz et al. 2013). Subjects will then practice the physiological measures and subjective questionnaires.

Experimental Session Timeline Participants will attend two experimental sessions lasting from 12:00 pm to 4:00 pm. Sessions are run from 12:00 pm to 4:00 pm to account for the diurnal rhythm of salivary cortisol—levels reach lowest levels at around midnight, start to rise at around 2:00 am to 3:00 am, reach a peak at around 8:30 am, and then slowly decrease back down to complete the cycle over 24 hours (Debono et al. 2009). Females in EFG will participate 1-8 days after first day of menstruation, at a time when both estradiol and progesterone levels are low (Barbieri et al. 2014). Females in the LFG will participate 9-14 days after first day of menstruation, at a time when estradiol levels are peaking or have just peaked, but progesterone levels remain low. The half-life of oral THC in infrequent users is about 1.3 days (Smith-Kielland et al. 1999). Therefore sessions will be scheduled with a minimum of 4 days to allow for washout.

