Upon arrival at each session at 12 pm, subjects will complete breath, drug, and pregnancy screens to verify compliance (Alco-Sensor® III, CLIAwaived, Inc. Rapid Drug Test Cup, CLIAwaived, Inc. Pregnancy Urine (Dip-Strip)). Subjects who test positive will be dismissed. Then, pre-capsule heart rate, blood pressure and body temperature will be measured, and subjects will complete subjective questionnaires measuring mood and drug effects (see below). Then a trained and certified research assistant will collect a saliva sample and draw two 5 ml samples of blood to be analyzed for ovarian hormones, estradiol and progesterone, and endocannabinoids, anandamide (AEA) and 2- arachidonoylglycerol (2-AG) (see assay section below). Then they will consume a capsule containing placebo or THC (7.5, 15 mg; see drug section below). Sessions will be run from 12:00 pm to 4:00 pm. Every 30 or 60 min throughout the session, heart rate, blood pressure, and body temperature will

be measured, a saliva sample will be taken and subjective questionnaires assessing mood, the Profile of Mood States (POMS, McNair et al., 1971) and State Anxiety Inventory (STAI, Spielberger et al. 1971), and drug effects, the Addiction Research Center Inventory (ARCI, Haertzen et al. 1963) and the Drug Effects Questionnaire (DEQ, Johanson and Uhlenhuth, 1980; Morean et al. 2013), will be administered (see timeline below).

Measures Physiological: Blood pressure will be recorded at half hour intervals (see timeline below) using portable Omron 10 Series Upper Arm Blood Pressure Monitor to measure cardiovascular effects of the drug. Body temperature will also be measured using a Metene Medical Forehead and Ear Thermometer. An electrocardiogram and thoracic impedance will be measured to examine effects on heart rate, heart rate variability, and respiration. Seven disposable self-adhesive electrodes will be placed on the participant's chest and back to produce a standard lead II configuration for ECG and standard tetrapolar electrode configuration for thoracic impedance. ECG and thoracic impedance measures will be amplified and processed by an integrated Mindware Bionex system (Mindware, Gahanna, OH). These measures will be used to both track the cardiovascular effects of the drug, and ensure participant safety.

Subjective: Participants will complete standardized questionnaires.

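### At the protocol's own 1.3-day half-life the 4-day minimum gap leaves about 12% of the THC, so it does not deliver the stated clearance; within one cycle the residue can also differ by phase group

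*Combined protocol and SAP*

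**What the plan says.** Under Experimental Session Timeline the protocol reports that "The half-life of oral THC in infrequent users is about 1.3 days" and draws the conclusion at once: "Therefore sessions will be scheduled with a minimum of 4 days to allow for washout". Aim 1 gives the purpose of the same interval in stronger terms: "Participants will attend two experimental sessions separated by at least four days, to allow for clearance of the drug".

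The Approach section sets the test windows: "EFG women will be tested 1 to 8 days since the first day of menstruation and LFG women between days 9 and 14". In the two sessions women "receive THC (15 mg THC) or placebo in counterbalanced order under double blind conditions". Blood and saliva are taken before the capsule at each session and are called baseline.

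The Orientation Session text advises light cannabis users to abstain for a week in order to pass the urine test. On arrival at each session the urine is screened, and "Subjects who test positive will be dismissed".

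The document gives no residual target, no maximum gap, and no statement on whether both sessions must fall in one cycle. The Statistical Analyses section names no period, sequence or carry-over term, and it does not say which session's baseline endocannabinoid values enter the model.

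**The concern.** The 4-day minimum is presented as following from the half-life, so it can be checked against that half-life. The check does not give clearance.

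Three things could be at stake. First, the placebo session of women who received THC first may not be free of study drug. Second, the two phase windows have different lengths (days 1 to 8 and days 9 to 14), so the longest possible same-cycle gap differs between the groups that Aim 1 compares. Counterbalancing balances order within each group; it does not make the gaps equal between groups. Third, study THC may be given 4 days before the second urine screen, although the protocol advises light users to allow a week to pass that screen. If study THC caused positive results, the dismissals would fall on THC-first women.

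**Working it through.** **Inputs.** Half-life 1.3 days and minimum gap 4 days (Experimental Session Timeline); windows of days 1–8 (EFG) and 9–14 (LFG), and 15 mg THC or placebo in counterbalanced order (Approach); measurement times 12:15 pm to 3:00 pm (session timetable).

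**Where the 4 days may come from.** No number of half-lives is stated, so the figure cannot be formally reproduced. It matches three half-lives rounded up (3 × 1.3 = 3.9 days), but that rule is inferred.

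**Residual.** With single-phase first-order elimination (an assumption), fraction left = 2^(−gap/1.3).

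| Gap (days) | Half-lives | Left |
|---|---|---|
| 4 | 3.08 | 11.9% (1.8 mg of 15 mg) |
| 5 | 3.85 | 7.0% |
| 6 | 4.62 | 4.1% |
| 7 | 5.38 | 2.4% |

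If 1.3 is rounded from 1.25–1.35, the 4-day figure is 10.9% to 12.8%.

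**Same-cycle gaps.** Count all day pairs inside each window that are at least 4 days apart.

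- EFG: four pairs at 4 days, three at 5, two at 6, one at 7. Mean gap 5.0 days. Mean residual (4×11.9 + 3×7.0 + 2×4.1 + 2.4)/10 = 7.9%.
- LFG: two pairs at 4 days, one at 5. Mean gap 4.33 days. Mean residual (2×11.9 + 7.0)/3 = 10.2%.

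The means assume equally likely pairs. If the rule is read as four full days between sessions (a 5-day difference), EFG has 5 to 7 days (7.0% to 2.4%) and LFG exactly 5 (7.0%).

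**Effect on the contrast, raw post-capsule levels.** Let E be the THC effect and r the residual, and assume response proportional to amount. Placebo-first women show E; THC-first women show E(1 − r). With balanced order the average is E(1 − r/2).

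- LFG: 10.2%/2 = 5.1% shrinkage.
- EFG: 7.9%/2 ≈ 3.9% shrinkage.
- Difference about 1.2 percentage points of E. The extreme case (11.9% against 2.4%, halved) is about 4.7 points.

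**Effect on the contrast, change from the pre-capsule value.** The residue is present before and after the placebo capsule. From 12:15 to 3:00 pm is 2.75 hours, or 0.115 days, over which it falls by 1 − 2^(−0.115/1.3) ≈ 6%. At a 4-day gap that is 0.06 × 11.9% ≈ 0.7% of E in THC-first women, or about 0.35% over both orders. The sign reverses: a declining residue makes the placebo change slightly negative, which slightly enlarges the contrast.

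**Which baselines can contain study THC.**

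| Order | THC-session baseline | Placebo-session baseline |
|---|---|---|
| THC first | before any study drug | after THC |
| Placebo first | after placebo only | before any study drug |

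Only one of the four cells is exposed, and it is not a THC-session baseline.

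**The case against.** The strongest reply is that a stated purpose of washout is not a promise of zero residue, that three half-lives is a judgement the sponsor may make, and that a urine screen on arrival guards the second session. Part of this stands. No residual target is breached, because none is stated, and the screen is a safeguard. But no cut-off is given, so the screen does not show absence of drug, and 12% left is not what a reader takes clearance to mean.

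A reader might go further and infer any of the following; the documents do not support them.

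- *Carry-over is necessarily tied to phase.* This holds only if both sessions fall in one cycle. Even then both groups share the 4-day minimum; what differs is the maximum and the equal-weight mean.
- *The bias works against the LFG hypothesis.* That needs raw levels and a proportional response. The protocol speaks mostly of increases and changes, for which the effect nearly vanishes and its sign reverses.
- *Aim 2's baseline is contaminated.* The THC-session sample precedes any study THC in both orders. Aim 2 is touched only if the placebo-session value of THC-first women is used or averaged in, and the effect on endocannabinoids could still be zero.
- *Equal gaps would make carry-over cancel.* Under the proportional model any phase difference in the THC effect is still scaled by (1 − r/2).
- *Study THC will cause positive screens.* The one-week advice concerns participants' own use. This is a tension to reconcile, not evidence.

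**Conclusion.** The point stands as a contradiction between a stated property and the protocol's own figure, with modest consequences. At the minimum gap about 12% of the dose remains, given a 1.3-day half-life and single-phase elimination; longer gaps leave less. If both sessions are in one cycle, the residue in the placebo session of THC-first women can differ by phase group (on average 10.2% in LFG against 7.9% in EFG with equally likely day pairs). The resulting shrinkage of the THC-placebo contrast is about 5% against 4% for raw levels, and close to nil for change from the pre-capsule value. The plan does not fix how the pre-capsule value enters the model, so neither the size within that range nor the direction is settled. Twelve per cent of the drug remaining does not show a 12% drug effect. The matter merits correction because the remedy is cheap, not because it threatens the main comparison.

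**What to change.** - Reconcile the clearance statement in Aim 1, the washout statement and half-life under Experimental Session Timeline, the two phase windows, and the urine-screen rule with its one-week advice. State the residual that the chosen gap leaves, and whether both sessions must fall in one cycle. No interval or scheduling rule is proposed here.
- Record each woman's gap in days and report it by phase group and order.
- Include session order and gap in the model. The gap should act on the placebo session of THC-first women; a term that is constant within a woman would leave the within-woman drug contrast unadjusted. With about 15 THC-first women per group (30/2), expect an imprecise estimate.
- State how the pre-capsule value enters each outcome, since this decides whether the residue matters.
- For Aim 2, use the pre-capsule AEA and 2-AG from the THC session.

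The cost is protocol wording, slightly more analysis work and a less favourable washout statement. No added participants or assays are needed.

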4. *The Drug Effects Questionnaire* (DEQ, Johanson and Uhlenhuth, 1980; Morean et al. 2013): This questionnaire contains visual analogue scales measuring subjective drug effects. It contains five questions, each associated with an anchored 100 mm line, on which participants indicate their response: "Do you feel any drug effect?" (rated from "none at all" to "a lot"), "Do you like the effects you are feeling now?" (rated from "not at all" to "very much"), "Do you dislike the effects you are feeling now?" (rated from "not at all" to "very much") "Are you high?" (rated from "not at all" to "very much") and "Would you like more of what you consumed, right now?" (rated from "not at all" to "very much"). This measure will be used another manipulation check to ensure the drug produced drug effects, but it will not be specific to a certain drug class.

5. *The Profile of Mood States* (POMS, McNair et al., 1971): This scale consists of 72 adjectives commonly used to describe momentary mood states. Participants indicate how they feel in relation to each of the 72 adjectives on a 5-point scale from "not at all" (0) to "extremely" (4). The questionnaire is comprised of eight subscales (Anxiety, Depression, Anger, Vigor, Fatigue, Confusion, Friendliness, Elation). Two summary scales are derived from the other scales: Arousal = (Anxiety + Vigor) - (Fatigue + Confusion); Positive Mood = Elation – Depression. This measure will be used to examine changes in state anxiety pre- and post-drug consumption.

Time	Activities	Measures
------	------------	----------

12:00 pm	Arrive, urine, and breath tests	Drug and pregnancy tests, breathalyzer
12:15 pm	Time point (baseline), saliva sample and blood draw	Subjective measures, HR, BP, Temp., saliva sample and blood draw
12:30 pm	Capsule (0, 15 mg THC)	
1:00 pm	Time point	Set up ECG, subjective reports, HR, BP, Temp.
1:30 pm	Time point	Saliva sample, subjective reports, HR, BP, Temp.
2:00 pm	Time point	Saliva sample, subjective reports, HR, BP, Temp.
2:30 pm	Time point	Saliva sample, subjective reports, HR, BP, Temp., EEfRT
3:00 pm	Time point	Saliva sample, subjective reports, HR, BP, Temp.
4:00 pm	Departure	End of session questionnaire, removal of electrodes

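### The ECG is attached 30 minutes after the capsule, so ECG heart rate, heart rate variability and (by inference) impedance-based respiration have no same-session pre-drug value

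*Combined protocol and SAP*

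**What the plan says.** The protocol and SAP are one document. Its physiological measures paragraph gives the purpose of the recordings: "An electrocardiogram and thoracic impedance will be measured to examine effects on heart rate, heart rate variability, and respiration". It also says they help to ensure participant safety. It describes one electrode set for both signals: "Seven disposable self-adhesive electrodes will be placed on the participant's chest and back".

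The timeline table places these events as follows:

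- **12:15 pm (baseline):** "Subjective measures, HR, BP, Temp., saliva sample and blood draw". Neither ECG nor impedance is listed.
- **12:30 pm:** capsule.
- **1:00 pm:** "Set up ECG, subjective reports, HR, BP, Temp".
- **1:30 to 3:00 pm:** heart rate, blood pressure and temperature at each half-hourly time point.
- **4:00 pm:** "End of session questionnaire, removal of electrodes".

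The session narrative agrees with the table. On arrival, "pre-capsule heart rate, blood pressure and body temperature will be measured", followed by questionnaires, saliva and blood, and then the capsule. It mentions no ECG before dosing.

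The Approach section lists heart rate among the secondary outcomes. Heart rate variability and respiration are not listed there, in the aims, or in the planned model.

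**The concern.** The aims are framed as THC-induced increases, and the ECG and impedance recordings are said to serve the study of drug effects. A signal first recorded half an hour after dosing has no starting point from which to measure an increase. For heart rate variability and respiration the protocol describes no other instrument, so no substitute baseline exists.

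Three things are lost for these measures: change from pre-drug, adjustment for a same-session baseline, and a check for pre-capsule differences between the early and late follicular groups. The last bears on the section on potential problems, which plans to covary pre-capsule differences between the groups. That cannot be done for a measure with no pre-capsule value.

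There is also a question about heart rate itself. The ECG is said to measure it, but the 12:15 pm value cannot come from an ECG that is not yet attached. The documents do not say which device supplies heart rate at each time point.

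**Working it through.** **1. Check the capsule time.** The saliva section gives post-drug samples at 1, 1.5, 2 and 2.5 hours. The table has saliva at 1:30, 2:00, 2:30 and 3:00 pm. Subtracting 12:30 pm gives 1.0, 1.5, 2.0 and 2.5 hours, an exact match, so the 12:30 pm capsule time is not an artefact of a broken table.

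**2. Place the ECG.** 1:00 pm − 12:30 pm = 30 minutes after the capsule. 1:00 pm − 12:15 pm = 45 minutes after the baseline time point.

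**3. Count pre-capsule readings per session.**

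| Measure | Scheduled before the capsule | Scheduled after |
|---|---|---|
| Heart rate (device not named) | 1 (12:15 pm) | 1:00, 1:30, 2:00, 2:30, 3:00 pm |
| ECG heart rate, heart rate variability | 0 | from 1:00 pm |
| Respiration (impedance) | 0 (inferred) | from 1:00 pm |

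The impedance row is an inference: the table names only the ECG, but one set of seven electrodes serves both signals. The EKG used for eligibility and the practice of physiological measures at orientation are not session baselines.

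**4. Look for the heart-rate device.** The only other cardiovascular device described is the cuff, "using portable Omron 10 Series Upper Arm Blood Pressure Monitor to measure cardiovascular effects of the drug". The text does not say that it supplies heart rate. Two cases follow. If one non-ECG device gives all the scheduled readings, the change score is sound and the ECG adds nothing to it. If later values come from the ECG and the 12:15 pm value from something else, the change score mixes methods.

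**5. Size the loss of precision.** Each woman has a THC and a placebo session, so the quantity analysed is in effect her THC-placebo difference. What matters is *r*, the correlation between the THC-placebo difference in baseline and that in outcome. Adjustment removes a share *r*² of the variance, which gives

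equivalent N = 60 / (1 − *r*²).

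Suppose baseline and outcome have equal variances, a same-session correlation ρ, and a correlation *s* between any two readings from different sessions. Then

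*r* = (ρ − *s*) / (1 − *s*).

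The documents give neither ρ nor *s*; both are assumed.

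| *s* | ρ | *r* | Equivalent N |
|---|---|---|---|
| 0.4 | 0.5 | 0.1/0.6 = 0.17 | 60/0.972 ≈ 62 |
| 0.6 | 0.7 | 0.1/0.4 = 0.25 | 60/0.9375 = 64 |
| 0.4 | 0.7 | 0.3/0.6 = 0.50 | 60/0.75 = 80 |

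**The case against.** The strongest reply is that nothing the plan lists as an outcome is lost. Heart rate is scheduled at 12:15 pm and at every later time point, separately from the ECG set-up. Heart rate variability and respiration are supporting measures, and the recordings also serve safety. The placebo session gives each woman's own comparison at the same clock times. All of this stands, and it limits the point to supporting measures. It does not restore the missing baseline: the placebo session removes stable differences between women, but not variation from one session to the next.

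A fair practical objection also stands. The half hour before the capsule already holds urine, pregnancy and breath tests, questionnaires, vital signs, saliva and a two-tube blood draw. Handling there could disturb baseline anxiety, or cortisol, which the Approach section names as the primary outcome. The order within the block therefore matters.

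Three stronger readings go too far:

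- **That heart rate has no baseline, or that its change score must mix devices.** A pre-capsule heart rate is planned in both sessions. Mixing is only a possibility, because the device is not named.
- **That attaching electrodes at 1:00 pm biases the results.** It coincides with the first post-capsule anxiety, heart-rate and blood-pressure readings, but it happens in both sessions and both groups. At most it adds noise, and the documents give no basis for sizing that noise.
- **That the missing baseline costs the equivalent of 20 to 58 women (80 to 118 against 60).** Those figures come from putting ρ = 0.5 to 0.7 straight into 60/(1 − ρ²). That ignores the crossover, which already removes stable between-woman variance, and would require *s* = 0.

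**Conclusion.** The gap is real: no ECG recording is scheduled before the capsule in either session, and the same is inferred for impedance. ECG-derived heart rate, heart rate variability and respiration can be compared between THC and placebo after dosing. They cannot be expressed as change, adjusted for a same-session baseline, or checked for group differences before dosing.

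The consequence is a modest loss of precision and interpretability on supporting measures. With *r* assumed at 0.17 to 0.5, a baseline would be worth about 62 to 80 women instead of 60 for those measures, and it would change nothing for cortisol. The listed secondary outcome, heart rate, is affected only if its readings come from different devices before and after the capsule. The timing finding does not depend on the assumed correlations. The change is still worth making, because a baseline that was never recorded cannot be recovered at analysis.

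**What to change.** 1. In both sessions, place the electrodes and record a short resting ECG and impedance segment before the capsule. Do this after the baseline questionnaires and saliva sample, so that handling does not disturb baseline anxiety or cortisol.
2. Name that segment in the analysis plan as the baseline for ECG heart rate, heart rate variability and respiration.
3. Name the heart-rate device and use the same one at all analysed time points. If it is the ECG, the resting segment is the heart-rate baseline; if it is another device, the 12:15 pm reading is.
4. If the order is not changed, state that the ECG and impedance measures are analysed as post-capsule values against placebo only.

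The equipment and electrodes are already in use. The cost is some extra minutes in an already full pre-capsule block, which may need a little more time, and longer electrode wear than the present span from about 1:00 to 4:00 pm.
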